5.3 Study population

The study will include healthy women that participate in the mammographic screening program at Södersjukhuset, Stockholm and at Skånes Universitetssjukhus, Lund, and have a negative screening mammogram. We will not include breast cancer patients as they receive a variety of drugs that might influence mammographic density. We are excluding women with no measurable density. This is because measurable density at study start is a prerequisite for being able to see reduction of mammographic density over time. We are not selecting women based on risk of breast cancer since we currently lack a reliable risk prediction model for Swedish standards.

5.4 Study length and study period

There are three studies [4,5,6] that used mammographic density change during one year as a proxy for tamoxifen effect. Two projects studied the association between mammographic density change in patients and prognosis and one study looked at density change among perfectly healthy woman and risk of breast cancer. All three studies came to the same result, approximately half of the treated participants respond to the therapy by a significant reduction in mammographic density after one year. Those that respond with a decreased mammographic density had a lower risk of breast cancer recurrence and a lower risk of breast cancer.

The main reason we conducted the Karisma I study was to investigate time to density change. Radiologists tell us that the time to density change is most probably much shorter than one year, probably only a couple of months. However, the issue of time to density change during tamoxifen therapy has never been addressed.

The results from Karisma I show that, regardless of dose, density decreases within 6 months by about 50% for one quarter of the participants, about 20% for another quarter and not at all for the other participants. This result implicates that tamoxifen intake during 6 months gives a measurable density change of responders; therefore, the treatment period in Karisma II are set to 6 months.

From a clinical point of view and for coming study (Karisma III) we will investigate the state of density change and decline of side effects 6 months after tamoxifen cessation in relation to doses. This will be done exploratory and only for the Lund-cohort.

The study period will be at least 14 months since we plan to run Karisma II at two sites successively:

Site	Karma Study Centre Lund	Karma Study Centre Stockholm/SöS					
Number of participants	Approximately 40	Approximately 1400					
First enrolment	November 2016	February 2017					
End of treatment	May 2017	December 2017					
End of follow	November 2017	December 2017					

5.5 Risk-benefit of frequent mammograms

Eligible study participants will only be women that have negative screening mammograms before entering the study, i.e. no abnormalities have been identified. The participants will have extra mammograms taken at 6 (all participants) and 12 (only Lund cohort) months after study entry. In order to reduce radiation exposure, the mammograms consist of 2 images instead of 4, which are standard at a screening examination. The images will be used for density measurement but radiologist will also screen them for abnormalities as in clinical practise. It could be that some few cancers are diagnosed at these extra visits, which should be seen as something that benefits the study participants.

If a suspected alteration is seen, women will receive the normal routine work-up for a suspected breast cancer, that is, additional ultrasound examination and a possible fine needle biopsy. Surgical interventions are only performed if a cancer is detected.

6 STUDY OBJECTIVES AND ENDPOINTS

6.1 Primary objective

Identify the minimal dose of tamoxifen that is non-inferior in its ability to reduce mammographic density compared to 20 mg tamoxifen.

6.2 Primary endpoint

Change in mammographic density and levels of side effects after 6 months. In particular, we will test for noninferiority in the proportion of women in the intervention arms (placebo, 1 mg, 2.5 mg, 5 mg, 10 mg) who have a density reduction as great as or greater (after 6 months) than the median density reduction in the 20 mg arm

6.3 Secondary objectives

Assess the drop-out level and the level of side effects in the intervention arms compared to the 20 mg arm.

6.4 Secondary endpoint

Drop-out rate. We will test for differences in the proportion of drop-outs after 6 months in the intervention arms compared to the 20 mg arm.

6.5 Teritary objectives

[figure not shown]
Relate levels of tamoxifen metabolites, proteins, lipids and hormones in blood and changes in breast tissue to tamoxifen doses. Measure genetic polymorphism in germline DNA and relate it to the other teritary objectives. Measure mammographic density and levels of side effects 6 months after tamoxifen cessation in relation to tamoxifen dose.

6.6 Teritary endpoints

Levels of tamoxifen metabolites, proteins, lipids and hormones in blood. Breast tissue changes. Genetic polymorphism in germline DNA. Mammographic density and levels of side effects 6 months after tamoxifen cessation

7 INVESTIGATIONAL PLAN

7.1 Overall study design

7.1.1 Invitation

Eligible women will be identified from women invited to mammography screening in Stockholm/Lund according to following:

- 1) A comprehensive study information about Karisma II will be sent to all women invited to mammographic screening at the collaborating sites a few days after screening invitation.
- 2) In connection with screening examination, interested women are invited to visit the Karma Study Centre (located within the screening facilities) to declare their interest of participation and to get further information about the study.

7.1.2 Pre-screening of eligibility of participation

At Karma Study Centre:

- 1) A Karma staff checks that the woman has read and understood the study information.
- 2) Volpara density measurement data are retrieved from the performed mammographic examination in order to see that the women meet inclusion criteria for density (≥4.5 % volumetric density)

3) Blood pressure is measured to ensure eligibility to participation.

If it at this stage turns out that the woman doesn't meet inclusion criteria or meet any of the exclusion criteria, she will have an explanation from investigator why she can't participate. A recording of non-participation is done in the Study file screening-list.

7.1.3 Baseline (Month 0)

Meeting with Investigator

- The investigator will explain the nature and aim of the study, its procedures, possible side effects, requirements and restrictions.
- The woman will sign the ICF before any further study related procedures are performed.
- A woman fulfilling the inclusion and exclusion criteria will be randomised to one of the six treatment arms; tamoxifen 20 mg, 10 mg, 5 mg, 2.5 mg, 1 mg or placebo. All treatments will be on a daily basis for 6 months
- The woman will receive a sufficient amount of IMP in order to take one tablet daily during 6 months
- Screening form, randomization number and other applicable information will be filled in by investigator in the eCRF.
- The participants will be asked if they allow to have two biopsies of the normal breast tissue taken at month 0 and 6. This is optional and complies with a separate study protocol (Protocol: Biopsy Karisma II)

Procedures at baseline

After meeting with investigator when ICF is signed and randomization is performed, the following will be obtained:

- In total 24 ml blood will be collected. The blood will be analysed for tamoxifen metabolites, plasma hormones, plasma proteins, metabolic markers. In addition, DNA will be extracted and plasma aliquots will be biobanked for later analyses.
- The participants will be asked to fill out two web-based questionnaires;
 - The Karma questionnaire including lifestyle factors that influence risk of breast cancer such as age at first birth, breast-feeding, etc., demographic, medical history, quality-of-life, and concomitant medication.
 - o Karisma II baseline questionnaire including general symptoms and tamoxifen related symptoms
- Pregnancy test (urine) will be offered women of childbearing age for safety
- Measurement of weight, length and waist
- Instructions are given on how to use and report events by the Karma-app
- Biopsy of the breast. This is optional and complies with an additional translational study protocol (Protocol: Biopsy Karisma II)

7.1.4 1 month after baseline (+2/-1 weeks)

• Karisma II follow up questionnaire including general symptoms, tamoxifen related symptoms, compliance and health care contact connected to possible side effects

- 7.1.5 3 months after baseline (+/- 2 weeks)
 - Karisma II follow up questionnaire including general symptoms, tamoxifen related symptoms, compliance and health care contact connected to possible side effects
- 7.1.6 6 months after baseline (+/- 2 weeks), End of treatment all participants, end of study SöS-cohort

Visit at Karma Study Centre:

- Karisma II follow up questionnaire including general symptoms, tamoxifen related symptoms, compliance and health care contact connected to possible side effects
- In total 24 ml blood will be collected. Planned analyses are tamoxifen metabolites, plasma hormones, plasma proteins, metabolic markers.
- Mammogram (one image per breast only for density measurement purposes)
- Measurement of weight, length and waist
- A 2nd biopsy will be performed if participation at baseline

End of study SöS cohort. The women will be informed that the study period now has ended and she will be called to mammography within the national screening program.

7.1.7 12 months after baseline (+/- 2 weeks), End of study Lund cohort

Visit at Karma Study Centre:

- Karisma II follow up questionnaire including general symptoms, tamoxifen related symptoms, compliance and health care contact connected to possible side effects
- Mammogram (one image per breast only for density measurement purposes)
- Measurement of weight, length and waist
- Meeting with Investigator (Group meeting)

The women will be informed that the study period now has ended and she will be called to mammography within the national screening program.

7.1.8 In between regular visits at the Karma Study Centre

In addition to the visits at the Karma Study Centre at baseline and 12 months, all participants will have access to web-based questionnaires at 1 and 3 months post baseline. The questionnaires will cover adverse events, change in concomitant medication and compliance.

The participants can at any time in between regular visit at the Karma Study Center contact the Karma Study Centre with questions and issues regarding adverse events, compliance and concomitant medications. The Karma Study Centre will give participants fast access to medical doctors in case of need.

7.1.9 Reminders

Women will receive e-mail/sms reminders regarding their upcoming appointment and/or web-questionnaire to complete.

Women not showing up at regular visits at the Karma Study Centre or fail to submit follow-up questionnaires will be contacted to ensure compliance and to ensure that no adverse events have occurred.

7.2 Dropouts

Participation in the Karisma II study is voluntary and the study participant may end her participation at any time. There may however be a scientific value to continue investigating the effects of tamoxifen after the participant discontinues her treatment to tamoxifen. Women that drop out after 1 week or more, will therefore be asked to still attend the planed follow-up questionnaires, blood sampling, exit-mammogram and biopsy if applicable. This is however not a mandatory request and the study participant is free to decline. The time limit of exit exams is set to 2 weeks after stop of medication.

7.3 The Karma Study Centre

Women participating in the Karisma II study will conduct all study specific activities, except the mammography, at the Karma Study Centre. The Karma Study Centre is located adjacent to the Breast and Mammography Unit at both Skånes Universitetssjukhus Lund and at Södersjukhuset. They were established in 2011 and many of the women invited to the Karisma II study are also part of the Karma Cohort and have thus visited the Karma Study Centre previously.

7.4 Choice of tamoxifen as risk-reducing medication

Tamoxifen is a selective estrogen receptor modulator (SERM), which means that it affects the way estrogen influences the breast tissue. Breast cancer development is closely linked to the exposure of the female breast tissue to female sex hormones, among them estrogen. The hormones increase the rate by which cells divide, proliferate, and thereby increase the risk of a deleterious mutation that could lead to cancer. Tamoxifen blocks the estrogen receptor and thereby estrogens effect on breast tissue.

The underlying mechanism driving tamoxifen to reduce breast density is not currently known, but rather one of the key scientific questions we struggle with right now. We do not know why more than 20% of the fibroglandular tissue "disappears" in approximately half of the woman treated with tamoxifen. It is not likely that the cells go into apoptosis but it could be that the reduced cell proliferation makes cells less radiolucent and therefore not seen on an x ray/mammogram.

Tamoxifen has been used in the treatment of breast cancer for more than 40 years and is generally well tolerated. There are several reasons why we chose to use tamoxifen in the preventive setting:

- The recently published American Association of Clinical Oncology (ASCO) clinical practice guideline on primary prevention of breast cancer, tamoxifen is one out of three suggested compounds and the only one suggested to be used in both pre- and post menopausal women [1].
- Tamoxifen is off patent and cheap (the cost is 10-20 that of aromatase inhibitors), thus is well suited from a health-economics perspective.
- Alternative drugs, e.g. aromatase inhibitors, have side effects such as severe joint pain that influence adherence to therapy.
- Aromatase inhibitors are not able to block the high production of estrogen seen in premenopausal women and are never used for younger women in the clinical setting. Thus aromatase inhibitors are not used for younger, premenopausal women. A woman identified with a very high risk of breast cancer at the age of 40 years should have the

possibility to start risk reducing medication and not have to wait until she enters menopause.

7.5 Choice of tamoxifen doses

In the *pilot study* we used 10 and 20 mg of tamoxifen. We choose the clinically accepted of 20 mg that has so far also been used in the preventive setting. By adding a dose of 10 mg we got an indication of both density response and severity of side effects.

There are currently no data supporting 10 mg of tamoxifen to have fewer and/or lower prevalence of side effects than 20 mg. This coincidence with what we saw in the *pilot study* but numbers were to small to make any significant conclusions. By adding 5 mg, 2.5 mg and 1 mg we believe that we will see a lower prevalence of side effects. The hypothesis that there is a linear dose – side effect relationship in tamoxifen therapy comes from the clinical experience in the early days of tamoxifen use. Initially the preferred dose was 40 mg/day but in the mid 1980s doses were lowered to 20 mg mainly because of the severe side effects of 40 mg. If we believe in a linear dose – side effects relationship, even lower doses should further reduce side effects.

7.6 Design of follow-up scheme

Experience from clinical practice using tamoxifen in the adjuvant setting and from the set up in the *pilot study*, indicates that side effects from tamoxifen typically occur within the first 3 months after initiation of treatment. The Karisma II study will therefore have frequent follow-ups during the first 3 months post baseline, including a follow up questionnaire after 1 and 3 month. Participants will also be instructed to contact Karma Study Center to report AE/side-effects whenever they occur.

7.7 Selection of study population

Eligible women will be identified from the Mammographic screening cohort, i.e. women age 40-74 years invited for screening at Södersjukhuset and University hospital in Lund during the inclusion period. Within this group of women, approximately 1/3 will be part of the Karma Cohort. The Karma Cohort is a prospective observational study including 70,877 women recruited in Stockholm and Region Skåne during 2010-2013. Women were recruited in to the Karma Cohort at screening centers in Lund, Landskrona, Helsingborg and at Södersjukhuset. Approximately 35 000 women were recruited from the Mammography department at Södersjukhuset and 10 000 from Mammography department in Lund. The only exclusion criteria were not being able to read and/or understand the informed consent form written in Swedish. For each participant we have gathered information on lifestyle factors, previous disorders, reproductive history, etc., through a web-based questionnaire. All participants have donated blood and allowed us to store mammograms. All Karma participants have signed an informed consent form allowing us to contact them to ask for participation in future studies.

Only including Karma participants in the study will slow down inclusion. We will therefore invite all women attending screening at Södersjukhuset and University hospital in Lund during the study period.

The rationale to exclude women with the lowest density is based on experience from our previous study of mammographic density reduction in patients on tamoxifen. In that study we had to exclude women with the lowest density since density change was not possible to measure in women with very low density. The cut off for inclusion is set to 4.5% density or more, measured by Volpara. The cut-off value is set to be sure that we will capture a change.

7.8 Inclusion criteria

To participate, the women must meet the following inclusion criteria:

- Attending the national mammography screening program, i.e. aged 40-74 and has performed a mammogram maximum 3 months prior to study inclusion
- Having a measurable mammographic density, i.e. ≥4.5 % density (volumetric) measured by Volpara
- Informed consent must be signed before any study specific assessments have been performed

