4.1 STUDY RATIONALE

For more than 40 years 20 mg of tamoxifen has been used in breast cancer patients to reduce the risk of *recurrence*. It has also been shown that 20 mg of tamoxifen reduces the *risk* of breast cancer in perfectly healthy women but that the treatment comes with side effects. [4] The side effects are probably one reason tamoxifen is not used in the preventive setting despite the substantial risk reducing effect. The aim of the Karisma II study is to identify the lowest

tamoxifen dose that could be used for *primary preventive* purposes, with a hypothesis that a lower dose will reduce the side effects.

Mammographic density is the white part of the mammogram and consist of glandular and connective tissue. The black, non-radiolucent part is fat. The more glandular and more connective tissues, the whiter the breast, and thus, the higher the risk of breast cancer [2]. Factors that influence risk of breast cancer are known to influence density. Hormone replacement therapy increases density and risk of breast cancer, while tamoxifen has the opposite effect [3]. The molecular basis for the tamoxifen-induced changes in breast density is sparsely understood. Consequently, a secondary aim in the Karisma trial is to investigate changes in tissue markers by comparing breast tissue biopsies sampled prior to and after six months of treatment with tamoxifen or placebo.

Mammographic density has been assessed in a nested case-control study within the IBIS-1 study, a randomised prevention study of tamoxifen vs. placebo. The density decrease, over the first 18 months, in 123 women diagnosed with breast cancer, was compared to 942 women without breast cancer [4]. Forty-eight per cent of the women treated with tamoxifen experienced a 10% or greater reduction in breast density and had a 63% reduction in breast cancer risk compared to women in the placebo group. In contrast, those who took tamoxifen but experienced less than a 10% reduction in breast density had no risk reduction.

Within the Karma group a parallel study has been conducted including breast cancer patients who where treated with adjuvant tamoxifen therapy [5]. Forty-eight per cent of the women experienced a decrease in density of > 20 % over a 12 month period and had a reduced breast cancer recurrence of 50%. These findings are fully supported by a very recent finding by a US group [6].

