7.9 Exclusion criteria

To participate, the women must not meet any of the following exclusion criteria:

- Being pregnant or planning to become pregnant during the study period
- Any previous or current diagnosis of breast cancer (including carcinoma in situ)
- Mammographic BI-RADS code 3 or above at baseline mammography, or at a diagnostic mammography during time of treatment (the first 6 months of the study)
- Any previous diagnosis of cancer with the exception of non-melanoma skin cancer and in situ cancer of the cervix
- Currently using *oral* oestrogen and progesterone based hormone replacement therapy
- Current use of hormone contraceptive with hormones, e.g. hormonal contraceptive pills, or progesterone implants. Hormonal intrauterine devices are accepted.
- A history of thrombo-embolic disease such as embolies, deep vein thrombosis, stroke, TIA or cardiac arrest.
- Known APC (Activated protein C) resistance, an inherited hemostatic disorder
- A history of major surgery of the breast, e.g. reduction or enlargement, which might affect density measurements
- A history of immobilization, e.g. using wheelchair
- Known uncontrolled diabetes
- Hypertension at baseline, defined as systolic pressure higher than 140 mm Hg and diastolic higher than 90 mm Hg
- Use of drugs that interfere with CYP2D6 expression such as Seroxat (paroxetine), Fontex (fluoxetin) and Zyban / Voxra (bupropion)
- Use of Waran (warfarin)
- Non-medical approved drugs against hot-flashes including phytooestrogen
- Not able to understand study information and/or informed consent

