7.11.7 Prior and concomitant therapy

Other therapy that is considered necessary for the subject's welfare may be given at the discretion of the Investigator.

- Women using drugs that interfere with CYP2D6 expression such as Seroxat (paroxetine), Fontex (fluoxetin), Zyban / Voxra (bupropion) are not allowed during the study or used at study enrolment.
- Oestrogen and progesterone based hormone replacement therapy (oral), hormone contraceptive with hormones, e.g. hormonal contraceptive pills, or progesterone implants are not allowed during the study or used at study enrolment.
- Waran (warfarin) is not allowed during the study or used at study enrolment
- Non-medical approved drugs against hot-flushes including phytoestrogen are not allowed during the study or used at study enrolment.

All concomitant therapy must be recorded in the eCRF. No other drug under investigation may be used concomitantly with the study medication. Medication will be coded according to WHO's Anatomical Therapeutic Chemical (ATC) classification.

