8.2 Birth control for women in fertile age

Premenopausal participants will be asked if they use any of the highly effective birth control methods mentioned below:

- 1. Hormonal contraception inhibiting ovulation.
 - a. Women on using exogenous female sex hormones will be excluded from the study since hormones affects mammographic density.
- 2. Intrauterine devices
 - a. Fully acceptable
- 3. Intrauterine hormone releasing systems
 - a. Fully acceptable since we do not believe that the low systemic hormone levels affects mammographic density. They do not influence the risk of breast cancer.
- 4. Bilateral tubal exclusion
 - a. Fully acceptable
- 5. Vasectomised partner
 - a. Fully accepted
- 6. Sexual abstinence
 - a. In most circumstances not an accepted method since the study continues for 6 months.

Methods #2-5 will be considered acceptable and in some few circumstances #6, depending on the wish of the participant.

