Appendix 14.3

Schedule of events Karisma II

Schedule of events Karisina II														
	Mx Screening	Baseline						End of treatment						End of study
Events								7						
Month		0	1	2	3	4	5	6	7	8	9	10	11	_12_
Selection of eligible study participants and														
invitation	~													
Mammography within screeningprogram	~													
Mammography for density measure								~						~
Visit at Karma Study centre		'						~						~
Screening for inclusion (inclusion and														
exclusion criterias checked)		/												
Informed consent signed		/												
Blood pressure		/												
Randomization		~												
Blood sampling		/						>						
Biometrics; Length, weight, waist		/						~						~
Pregnancy test (if applicable)		/												
Biopsy (optional)		~						~						
Interview (optional)		~						~						~
IMP administration		/												
Drug acountability check								~						
Karma Baseline questionnaire		~												
Karisma Baseline questionnaire		~												
Follow up questionnaire (sideeffects,														
compliance, concomitant medication)			~		~			~						~
AE-reporting (spontanously)		day2	~	~	~	~	~	~	~	~	~	~	~	~
Check screen mx for exclusion (code 3,4 or 5)	day2												

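### The hormone exclusion is judged at enrolment, but baseline density comes from a mammogram up to 3 months older; a fall from stopping hormones would count as response in any arm, with a probably small bias toward non-inferiority

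*Protocol*

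**What the plan says.** **Baseline image.** Inclusion (Protocol 7.8) requires that the woman "has performed a mammogram maximum 3 months prior to study inclusion". At pre-screening (7.1.2), "Volpara density measurement data are retrieved from the performed mammographic examination" to check eligibility. The row "Mammography for density measure" in Appendix 14.3 is ticked at months 6 and 12 only, and 5.5 agrees: "The participants will have extra mammograms taken at 6 (all participants) and 12 (only Lund cohort) months after study entry". No density image is scheduled at month 0. The documents never state outright that the screening image supplies baseline for the primary endpoint, but no other pre-treatment image exists.

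**Hormone rule.** Protocol 7.9 excludes women now taking oral hormone replacement and, separately, "Current use of hormone contraceptive with hormones, e.g. hormonal contraceptive pills, or progesterone implants". Section 7.11.7 repeats the rule for both classes, ending "hormonal contraceptive pills, or progesterone implants are not allowed during the study or used at study enrolment". Neither section looks back to the date of the image.

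**Reason for the rule.** Section 8.2, on contraception: "Women on using exogenous female sex hormones will be excluded from the study since hormones affects mammographic density". Section 4.1 gives a direction for one class: "Hormone replacement therapy increases density and risk of breast cancer, while tamoxifen has the opposite effect".

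**Analysis.** A responder (Protocol 10.6.2, SAP 6.3) is a woman whose fall from baseline to 6 months exceeds the median fall in the 20 mg arm. Hormone exposure does not enter that rule. HRT status appears once, as a covariate in the sensitivity imputation model (SAP 6.9). SAP 6.7 has confounders in its title but names no hormone adjustment.

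**The concern.** The exclusion protects the density measurement, yet it is checked on a different date from the measurement it protects. A woman on oral hormone replacement at the screening image who stops before enrolment meets every written criterion. Her baseline is read on hormones and her 6-month value off them. By the protocol's own statement about hormone replacement, the expected change is a fall, the same direction as the tamoxifen effect.

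Hormonal contraceptives may raise the same problem, but the documents say only that hormones affect density. They give no direction for contraceptives.

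Such a fall does not depend on dose. It adds responders to a weak arm and also shifts the 20 mg median that sets the threshold. Both effects narrow the gap between a weak dose and 20 mg, which in a non-inferiority comparison favours the weak dose. SAP 6.1 and 6.9 already accept that the ITT analysis, run with last observation carried forward, is likely to lean toward equivalence. This would add to that lean.

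**Working it through.** **1. Inputs (Protocol 10.6.3, SAP 6.6).** 168 evaluable women per arm, one-sided 98.5% limit (alpha 0.015), power 80%, 50% responders in the 20 mg arm, true difference 0, margin 16.7 points, 30% drop-out.

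**2. The plan's own figure.** n = (2.170 + 0.842)² × (50×50 + 50×50) / 16.7² = 9.070 × 5000 / 278.89 = 162.6, so 163. The plan states 168, within about 3%. Power at 168 is 81.4%. Then 168 / 0.70 = 240 per arm, and 240 × 6 = 1,440. The plan's figures are close enough to use 168 and alpha 0.015 below.

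**3. Model for the bias.** Assumptions not given in the documents:
- A share q of every arm are stoppers. Randomisation makes q equal across arms on average.
- A proportion r of stoppers pass the threshold, whatever their dose.
- In all other women, change is normal. The dose effect is the shift that gives 33.3% against 50% when q = 0: z(0.500) − z(0.333) = 0.432 SD.
- The threshold is the 20 mg median, so that arm stays at 50%.

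Non-stoppers above the threshold in the 20 mg arm: s = (0.5 − qr) / (1 − q).
Responders in the weak arm: p = qr + (1 − q) × Φ(z(s) − 0.432).
Chance of declaring non-inferiority: Φ((0.167 − (0.5 − p)) / SE − 2.170), with SE = √(0.25/168 + p(1 − p)/168).

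This uses the confidence-limit rule on which the sample size rests, in the normal approximation. It does not model the Fisher test named in SAP 6.3 or the resampling step in SAP 6.7.

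**4. Worked case, q = 5%, r = 1.** s = 0.45 / 0.95 = 0.4737, and z(s) = −0.066. Φ(−0.066 − 0.432) = 0.3094. p = 0.05 + 0.95 × 0.3094 = 0.3439. The apparent difference is 15.6 points instead of 16.7. SE = 0.0532. Φ((0.167 − 0.1561)/0.0532 − 2.170) = 2.5%.

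**5. Results for a dose exactly at the margin (nominal 1.5%).**

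| q | Weak-arm responders, r = 1 | Apparent difference, r = 1 | False non-inferiority, r = 1 | False non-inferiority, r = 0.75 |
|---|---|---|---|---|
| 0 | 33.3% | 16.7 | 1.5% | 1.5% |
| 1% | 33.5% | 16.5 | 1.7% | 1.6% |
| 2% | 33.7% | 16.3 | 1.8% | 1.8% |
| 5% | 34.4% | 15.6 | 2.5% | 2.3% |
| 10% | 35.5% | 14.5 | 4.0% | 3.5% |
| 15% | 36.8% | 13.2 | 6.4% | 5.2% |

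**6. Away from the margin.** If the weak dose truly has 25% responders, q = 15% with r = 1 lifts it to 30.7%, and the false non-inferiority rate is still below 0.4%.

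**The case against.** **Little time to stop.** Protocol 7.1.1 has women visit the study centre in connection with screening, inside the same facility, and Appendix 14.3 puts the check of the screening images at day 2. If enrolment usually follows the image within days, few women can have stopped in between. This stands as an argument about size: 3 months is a ceiling. It remains the permitted interval, and nothing in the criteria enforces a shorter one.

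**A stopper is not automatically a responder.** This stands. A reader might infer that every such woman is scored as a tamoxifen responder. She is one only if her fall exceeds the 20 mg median, and the documents do not say how far or how fast density falls after stopping. The r = 1 column is an upper case.

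**Randomisation balances these women.** True on average, so a reader who inferred confounding between arms would be wrong. Balance does not prevent dilution. The placebo arm would reveal a large background fall, but would neither identify its cause nor correct the comparisons.

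**Checking hormone use on the image date does not close the gap.** This also stands. Study information goes out before screening (7.1.1), so a woman could stop days before the image and still have raised density. That is why a stop date is needed as well as a yes or no.

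**Excluding such women from the primary analysis.** Because exposure at the image precedes randomisation, a reader might think they could simply be dropped. The primary analysis is declared ITT (Protocol 10.6.2, SAP 6.1), and the existing records are not said to capture hormones stopped before enrolment. The documents support a sensitivity analysis, not a change to the primary set.

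**Conclusion.** The gap is in the text. Eligibility looks at hormones from enrolment onward, baseline density can predate that by up to 3 months, no month-0 image is taken, and neither the responder rule nor the primary analysis corrects for it. The direction is toward non-inferiority.

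The size is probably small. With 1% to 2% stoppers, the error for a dose exactly at the margin rises from 1.5% to about 1.7% to 1.8%. It takes one woman in ten, all passing the threshold, to reach 4.0%. These figures rest on an assumed share, an assumed pass rate and a normal model, because the documents give neither the number of stoppers nor the size of their fall. The direction is documented for hormone replacement only. The documents do not support a reading that the trial's conclusion is materially at risk: for a dose well short of the margin, the effect is negligible. The point merits action because it is cheap to close, not because the expected bias is large.

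**What to change.** 1. Reconcile Protocol 7.8 and 7.9 so that the existing hormone eligibility criterion, with its list of hormones unchanged, is also assessed on the date of the mammogram that supplies baseline density. The concomitant-therapy rule in 7.11.7 need not change.
2. Add one dated question at the eligibility check: hormone use at the image and, if stopped, the stop date. The baseline questionnaire covers concomitant medication (7.1.3) but is not said to record earlier use by date, and some women may stop shortly before the image.
3. Keep all randomised women in the ITT primary analysis. In SAP 6.5.1, prespecify a sensitivity analysis of the responder comparison that excludes, or adjusts for, women exposed at or shortly before the baseline image. Define the look-back period before unblinding and report the number of such women by arm.

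Cost: a few volunteers become ineligible, one question is added, and there is one more sensitivity analysis. The sample size does not change. Protocol version 2.1 predates Stockholm recruitment, where about 1,400 of the 1,440 women were planned, so at that version the change could have covered nearly all of them.
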